using the more feasible surrogate outcome of cancer progression beyond AJCC 7th edition stage T1a, the most curable stage. They also emphasized the importance of understanding patient preferences for more or less frequent surveillance. More specifically, while some stakeholders felt strongly that the most important imperative was to identify cancer early at all costs, others were concerned that more intensive surveillance would aggravate distress and anxiety associated with having a potentially cancerous nodule and “not knowing” its status. Listening to these views prompted us to expand the study design to include the survey of patient-reported outcomes during the surveillance period (Aim 2). Stakeholder partners representing clinicians, health systems, and payers had additional concerns about resource utilization, radiation exposure and adherence, providing the incentive for studying these outcomes in Aims 3 and 4.

Study Aims

Aim 1. Among individuals with small pulmonary nodules identified either incidentally or by screening, compare more versus less intensive surveillance for the number of cancerous nodules that progress beyond AJCC 7th edition stage T1a or AJCC 8th edition stage T1b. Approach: search EHRs and establish linkages with local and statewide cancer registries to ascertain the primary outcome and secondary outcomes of timeliness of lung cancer diagnosis and overall survival of patients in each study arm who prove to have a cancerous nodule.

Aim 2. Compare patient-reported outcomes of emotional distress, anxiety, general health status and satisfaction with the evaluation process. Compare provider satisfaction with the surveillance protocol and the evaluation process. Approach: survey patients via Internet or mail, using validated measures of emotional distress (IES-R), anxiety (STAI-6), and general health status. Patients will be surveyed at 1-2 and 13-24 months following nodule identification, and upon completion of surveillance to assess outcomes over time. Radiologists and ordering providers

(pulmonologists and thoracic surgeons) will be surveyed at the start of patient enrollment and at during the follow-up period. In addition, primary care physicians may be surveyed at the start of patient enrollment and during the follow-up period.

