All CT scans performed for pulmonary nodule surveillance should be done using low radiation-dose technique, however, this vitally important aspect of imaging quality and safety is often overlooked during CT surveillance of lung nodules. Guidance on low radiation-dose techniques will be provided to each site and the study protocol will strongly recommend the use of these or equivalent low radiation-dose protocols for all follow up CT scans. During the first 3 months of the trial, site project coordinators will review the CT examinations and record radiation dose metrics (CT Volumetric Dose Index [CTDI vol] and Dose Length Product [DLP]) on a large sample of chest CTs performed at their site (10-50% depending on population; 100% for California hospitals as these data are included in the medical record by law) to determine if the

CTs were performed using appropriate techniques. Staff will be trained in radiation dose extraction techniques. Radiation dose metrics will be calculated monthly by site, provided to the Data Coordinating Center, and reviewed during regular meetings. Initiatives to ensure compliance with low-dose examinations will include site visits and radiology-specific lectures.

Table 4: Definition and Source Information for Outcomes, by Specific Aim				
Aim	At Risk	Outcome	Definition	Source
1	Participants with cancerous nodules	AJCC 7 th edition Stage >T1a or AJCC 8 th edition stage >T1b	Tumor size >20 mm at time of resection or radiotherapy.	Cancer Registry, EHR
		Time to diagnosis and treatment	Time to diagnosis and time to treatment with surgery, radiotherapy or chemotherapy, measured from date of index CT scan to date of first treatment.	
		Survival	Measured from date of index CT scan to death or censoring.	
2	All patients with nodules and access to email	Nodule-related distress	Measured with validated IES-R. Assessments performed 1-2 months after index CT scan, at 13-24 months, and at end of follow-up.	Self-administered web survey
		Anxiety	Measured with validated STAI-6. Assessments performed 1-2 months after index CT scan, at 13-24 months, and at end of follow-up.	
		General health status	Assessments performed 1-2 months after index CT scan, at 13-24 months, and at end of follow-up.	
		Satisfaction with evaluation	Measured with novel items, Likert-type scale. Assessment performed at 13-24 months and at the end of follow-up	

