The primary study objectives include, among individuals with small pulmonary nodules identified either incidentally or by screening, comparing more vs. less intensive CT surveillance for the progression of cancer beyond AJCC 7th edition stage T1a disease (or T1b in the AJCC 8th edition) (Aim 1), nodule-related emotional distress (Aim 2), health care resource utilization and exposure to diagnostic radiation (Aim 3), and overall adherence with the recommended surveillance protocol (Aim 4).

The secondary objectives include comparing more vs. less intensive CT surveillance for the timeliness of lung cancer diagnosis and overall survival of patients in each study arm who prove to have a cancerous nodule (Aim 1), patient general health status and satisfaction with the evaluation process and the provider satisfaction with the surveillance protocol and the evaluation process (Aim 2), and adherence to use of low radiation-dose techniques (Aim 4). In general, we hypothesize that more intensive follow-up will result in more CT imaging (by design), greater radiation exposure, more downstream testing, greater anxiety and emotional distress, slightly shorter times to cancer diagnosis, and worse adherence to follow-up, and no effect on cancer stage distribution or overall survival.

Primary endpoints:

Aim 1: Proportion of lung cancers that are greater than 20mm

- Measured as progression beyond AJCC 7th edition T stage of T1a or, equivalently, AJCC 8th edition T stage of T1b

Aim 2: Nodule-related anxiety and emotional distress at 1-2 months, 13-24 months, and ≥25 months after nodule identification

- Measured using the IES-R and STAI-6

Aim 3:

1. Health care resource utilization within 26 months following nodule identification
 - Number of visits within 26 months of nodule identification, including the following exams (separate analyses by type of exam):
 - Chest CT scans
 - Chest x-rays
 - PET or PET/CT scans
 - Biopsies (look separately and together): Bronchoscopic biopsy, percutaneous biopsy, surgical biopsy/resection, extrapulmonary biopsy.
 - We will not include any exams after the date of cancer diagnosis, but will include biopsy that led to the cancer diagnosis
2. Serious complications within 7 days and within 30 days of a chest CT, chest x-ray, PET or PET/CT scan, or biopsy (bronchoscopic biopsy, percutaneous biopsy, surgical biopsy/resection, extrapulmonary biopsy) performed within 26 months of baseline CT:
 - Pneumothorax

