 - Pneumothorax requiring tube thoracostomy
 - Bleeding (pulmonary hemorrhage)
 - Acute respiratory failure
 - Acute renal failure
 - Allergic reaction to iodinated contrast material requiring hospitalization
 - Acute myocardial infarction
3. Cumulative radiation dose measured by DLP and effective dose

- Including radiation exposure from surveillance and diagnostic imaging following baseline CT scan through 2 years of follow-up (including 24 month exams).

Aim 4: Adherence with the recommended surveillance protocol

1. Radiologist adherence to assigned protocol
2. Physician adherence to ordering test
3. Patient adherence
 - a. Adherence to first recommended surveillance exam
 - b. Adherence to full protocol

Secondary endpoints:

Aim 1:

1. Proportion of lung cancers that are greater than 20mm, N0, MO
 - Measured as progression beyond AJCC 7th edition TNM stage of T1aN0M0 or AJCC 8th edition stage of T1bN0M)
2. Timeliness of lung cancer diagnosis
 - Measured as time from date of index CT scan to confirmed lung cancer diagnosis, defined as histologic confirmation via pathology, among individuals diagnosed with lung cancer.
3. Timeliness of lung cancer treatment
 - Measured as time from date of index CT scan to date of first treatment including surgery, radiotherapy or chemotherapy, among individuals diagnosed with lung cancer. If a patient receives no treatment, we will censor at end follow-up.
4. Overall survival of patients who prove to have a cancerous nodule,
 - Measured from date of index CT scan to death or censoring among individuals diagnosed with lung cancer.

Aim 2:

1. Patient general health status measured at 1-2 months, 13-24 months, and ≥ 25 months after nodule identification
2. Patient satisfaction with the evaluation process measured at 13-24 months and ≥ 25 months after nodule identification
3. Ordering specialist, primary care, and radiologist knowledge attitudes and beliefs about existing guidelines for pulmonary nodule evaluation measured at baseline
4. Provider satisfaction with the surveillance protocol and the evaluation process measured during the follow-up period

Aim 4: Adherence to use of low radiation-dose techniques

Hypotheses:

We specify the following hypotheses by aim:

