H1a: Among participants with nodules that prove to be cancerous, less intensive surveillance will be non-inferior to more intensive surveillance for: (a) the frequency of cancer progression beyond AJCC 7th edition stage T1a disease (or T1b for AJCC 8th edition) and (b) the frequency of cancer progression beyond AJCC 7th edition TNM stage T1aN0M0 (or T1bN0M0 for AJCC 8th edition). In addition, among participants with *lung nodules*, less intensive surveillance will be non-inferior to more intensive surveillance for: (a) the frequency of cancer progression beyond AJCC 7th edition stage T1a disease (or T1b for AJCC 8th edition); and (b) the frequency of cancer progression beyond AJCC 7th edition TNM stage T1aN0M0 (or T1bN0M0 for AJCC 8th edition).. Furthermore, in exploratory analyses for HTE, we hypothesize that individuals who are most likely to benefit from more intensive surveillance will include older people, people with larger nodules (>8 mm), patients with solid or part-solid nodules (compared with non-solid

nodules), and individuals with nodules detected by screening (compared with individuals who have nodules that are incidentally detected).

H1b: Among participants with nodules that prove to be cancerous, more intensive surveillance will result in more timely diagnosis than less intensive surveillance.

H1c: Among participants with nodules that prove to be cancerous, less intensive surveillance will be non-inferior to more intensive surveillance for overall survival. Among participants with lung nodules, less intensive surveillance will be non-inferior to more intensive surveillance for overall survival.

H2a: Among all participants with a lung nodule ≤ 15 mm, more intensive surveillance will be associated with greater levels of emotional distress and state anxiety at 13-24 months, but levels of distress and anxiety similar to less intensive surveillance at 1-2 months and ≥ 25 months.

H2b: Among all participants with a lung nodule ≤ 15 mm, more intensive surveillance will be associated with scores similar to less intensive surveillance for general health status at 1-2 months, 13-24 months and ≥ 25 months.

H2c: Among participating radiologists and pulmonologists, satisfaction with the surveillance protocol will be greater among those who practice at institutions assigned to the less intensive protocol.

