H3a: Among all participants with a lung nodule ≤ 15 mm, more intensive surveillance will be associated with greater nodule-related resource utilization, including more frequent use of CT scanning, PET scanning and invasive biopsy.

H3b: Among all participants with a lung nodule ≤ 15 mm, more intensive surveillance will be associated with a greater number of serious complications related to invasive procedures, including pneumothorax, pneumothorax requiring tube thoracostomy, bleeding, acute respiratory failure, acute renal failure and acute myocardial infarction.

H3c: Among all participants with a lung nodule ≤ 15 mm, more intensive surveillance will be associated with greater total exposure to diagnostic radiation than less intensive surveillance.

H4: Among all participants with a lung nodule ≤ 15 mm, more intensive surveillance will be associated with worse adherence to the surveillance protocol than less intensive surveillance, when measured at the level of the interpreting radiologist, the ordering provider and the patient.

Analysis Plan

In most cases, the unit of analysis will be the individual patient. All primary analyses will be by intention to treat, although we will also perform sensitivity analyses by surveillance imaging actually received. The intention to treat population will include all patients with qualifying nodules, even ones who do not undergo surveillance as the initial step in their evaluation (i.e., patients that proceed directly to tissue diagnosis). Sensitivity analyses will evaluate outcomes by strategy recommended and by surveillance imaging received.

Descriptive statistics will be generated for continuous variables (e.g., mean, standard deviation, median, range) and categorical variables (frequency) at baseline and follow-ups when appropriate. Bivariate analyses will include comparisons of means or medians (as appropriate) for continuously measured variables, cross tabulations of categorical variables, and Kaplan-Meier plots for time to event outcomes. Count outcomes, such as the number of procedure-related complications, will be treated as Poisson random variables. Analysis of time to

diagnosis, treatment, and survival will use Cox regression, after checking the proportionality assumption by creating log-minus-log plots.

H1a - Primary endpoint –lung cancer stage >T1a at diagnosis:

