To examine whether among participants with cancerous nodules, less intensive surveillance will be non-inferior to more intensive surveillance for the frequency of cancer progression beyond AJCC 7th edition stage T1a (or T1b for 8th edition) disease, we will use hierarchical logistic regression that includes random site effects to account for clustering of patients within sites and to capture institutional characteristics that are not explicitly modeled. Hierarchical logistic regression models will be fitted with and without adjusting for potential confounders including age, gender, ethnicity/race, smoking, body mass index (BMI), baseline nodule size, and any facility-level factors balanced during the randomization.

We will conduct a main analysis and several sensitivity analyses.

1. The main intent to treat analysis will include all enrolled participants in both study arms
2. A modified intent to treat sensitivity analysis will include:
 - a. For integrated healthcare systems, all active members
 - b. For other systems, patients who have at least one follow-up visit
3. On treatment sensitivity analyses will include those who met the definition of adherence to first recommended test and to overall surveillance protocol
4. We will conduct another sensitivity analysis using all nodules, instead of cancerous nodules, as the denominator to evaluate rates instead of proportions, given some concern about the potential for overdiagnosis in the more intensive arm. However, we are concerned about evaluating rates among all nodules due to the potential for differential enrollment of very small, likely insignificant nodules across sites. Inclusion of these nodules in overall rates will inflate the denominator without an increase in

numerator, resulting in smaller rates. Thus, we will evaluate variation in lung cancer rates across site within arms. Significant heterogeneity among the sites will provide evidence that the rates may be unreliable due to differential enrollment.

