Timeliness of treatment: To investigate whether among participants with cancerous nodules, less intensive surveillance will be non-inferior to more intensive surveillance for timeliness of treatment, we will restrict our analysis to participants with cancerous nodules and use Cox regression models where time from initial nodule identification to treatment is the outcome variable. Patients who die or do not receive treatment will be censored at end of follow-up. We will consider using competing risk models, as necessary.

H1c: Secondary endpoint

Survival: To investigate whether among participants with cancerous nodules, less intensive surveillance will be non-inferior to more intensive surveillance for overall survival, we will restrict our analysis to participants with cancerous nodules and use Cox regression models where time from initial nodule identification to death as the outcome variable. Patients will be censored at end of follow-up.

For all time-to-event analyses, clustering by site will be handled by specifying subjects nested within each cluster and using robust sandwich estimators for statistical inferences.⁶¹ The proportionality assumption will be checked by creating log-minus-log plots. To explore whether individuals who are most likely to benefit from more intensive surveillance, subgroup analyses will examine the effect of age (using the median and/or quartile values as cut points), nodule size (>8 mm), nodule attenuation (solid or part-solid nodules compared with non-solid nodules), and mode of detection (detected by screening compared with incidentally detected).

Analytically, we will include interaction terms between each of these factors with treatment in the models, respectively. For significant interactions, we will also conduct subgroup analysis to explore the treatment effects in corresponding subgroups. Since the study is not powered to test interaction terms, these analyses will be exploratory. For H1b, to study whether among participants with cancerous nodules, more intensive surveillance will result in more timely diagnosis and treatment than less intensive surveillance, we will adopt similar strategy used for comparing overall survival described above.

H2a:

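### H1c claims non-inferior survival in all participants with nodules, but survival is analysed only in those later diagnosed with cancer, and no survival margin is given.

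*Combined protocol and SAP*

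**What the plan says.** All references are to the combined protocol and SAP.

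**Survival hypotheses.** H1c in the Hypotheses section first claims non-inferior survival for participants whose nodules prove cancerous. It then adds: "Among participants with lung nodules, less intensive surveillance will be non-inferior to more intensive surveillance for overall survival".

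**Survival definitions and analysis.** All of these are limited to cancer patients:
- Study Aims, Aim 1, and the secondary objectives: "overall survival of patients in each study arm who prove to have a cancerous nodule".
- Table 4: the population at risk for Aim 1 is participants with cancerous nodules, and survival is "Measured from date of index CT scan to death or censoring".
- Secondary endpoints, Aim 1, item 4: "Measured from date of index CT scan to death or censoring among individuals diagnosed with lung cancer".
- H1c: Secondary endpoint, Survival: "we will restrict our analysis to participants with cancerous nodules and use Cox regression models where time from initial nodule identification to death".

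The general Analysis Plan says that time to "diagnosis, treatment, and survival will use Cox regression" but names no population.

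**Effect of arm on diagnosis.** The Objectives expect more intensive follow-up to give "slightly shorter times to cancer diagnosis". Sensitivity analysis 4 for H1a uses all nodules as the denominator "given some concern about the potential for overdiagnosis in the more intensive arm".

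**Timeliness (H1b).** The Hypotheses section and the last sentence of the time-to-event text state that more intensive surveillance is superior. The paragraphs on timeliness of diagnosis and of treatment instead set out to show that less intensive surveillance is non-inferior.

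**The concern.** There are three problems.

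1. A stated secondary hypothesis cannot be tested as written. It has no analysis, and without a margin a non-inferiority claim has no decision rule.
2. The survival analysis that is specified conditions on something that happens after randomisation. The clock starts at the index CT, but a patient enters the subset only by living long enough to be diagnosed. The interval from index CT to diagnosis is therefore free of deaths by construction, and it is longer in the arm that diagnoses later. If one arm also finds more indolent cancers, the two subsets differ in prognosis. Either mechanism can move the hazard ratio from 1 when surveillance changes nobody's date of death.
3. Superiority of one arm and non-inferiority of the other are different tests. A result could satisfy one and fail the other, so the H1b wording leaves the choice open.

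At stake is how a secondary survival result is read. The primary outcome is not affected by this point. The Aim 1 Outcomes section already warns that follow-up for lung cancer deaths will be limited.

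**Working it through.** **Is there a margin that could be borrowed?** The sample-size section gives only 5 percentage points, for tumor progression. It behaves as a non-inferiority margin for that outcome:
- Cluster size 888/24 = 37, so the design effect is 1 + 36 × 0.01 = 1.36.
- Effective patients per arm: 444/1.36 = 326.5.
- Standard error: √(2 × 0.05 × 0.95/326.5) = 0.0171.
- Power: Φ(0.05/0.0171 − 1.96) = 83.4%, against 83% stated.

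No margin, power or death count is given for survival, and a 5-point difference in tumor stage does not convert to a hazard ratio.

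**Death-free time in the cancer subset.** The documents give neither times to diagnosis nor mortality, so these are assumptions: exponential time to diagnosis with mean *m* months (d = 1/m); diagnosis within 24 months; yearly mortality of 5% before diagnosis and 15% after, giving monthly hazards λ0 = −ln(0.95)/12 and λ1 = −ln(0.85)/12; no effect of arm on mortality. At time *t* the subset contains:
- not yet diagnosed (t < 24): U(t) = d/(d+λ0) × [e^(−(d+λ0)t) − e^(−(d+λ0)·24)], with no deaths possible;
- diagnosed and alive: X(t) = d·e^(−λ1·t) × [1 − e^(−(d+λ0−λ1)·min(t,24))]/(d+λ0−λ1), with hazard λ1.

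The observed hazard is λ1·X/(U+X), which is lower where diagnosis is later. Solving the expected Cox score gives these hazard ratios (less v more intensive):

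| Mean time to diagnosis, more v less (months) | Deaths to 24 months | To 36 months | To 48 months |
|---|---|---|---|
| 6 v 7 | 0.962 | 0.975 | 0.981 |
| 6 v 9 | 0.904 | 0.937 | 0.952 |
| 6 v 12 | 0.845 | 0.899 | 0.922 |

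With equal mortality before and after diagnosis, so that no date of death can change, the 24-month column is 0.965, 0.910 and 0.854. An all-participant analysis then gives 1.00.

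**Scale.** About 21.7% of the subset die by 24 months: 960 × 0.217 = 208 deaths. The standard error of the log hazard ratio is √(4/208) = 0.139. If the ICC of 0.01 also applied to death, the design effect would be 1 + (960/24 − 1) × 0.01 = 1.39 and the standard error √(4 × 1.39/208) = 0.163. For 6 v 7 months, |ln 0.962| = 0.039, about a quarter of a standard error. The 6 v 9 and 6 v 12 rows assume gaps larger than the plan's expectation of slightly shorter times.

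**Overdiagnosis, acting alone.** Assume 480 cancers per arm and 20% dead (96 deaths) in each, with extra non-fatal cancers found only in the more intensive arm. The apparent ratio is ln(1 − 96/480)/ln(1 − 96/(480(1+e))), which is 1.06, 1.11 and 1.22 for e = 5%, 10% and 20%.

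**Both acting.** With 6 v 7 months, deaths to 24 months, and 10%, 20% or 30% indolent cancers of which half are missed in the less intensive arm, the planned ratio is 1.00, 1.03 and 1.07.

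**What an all-participant analysis could show.** Assume 32,000 participants, 3% with cancer, 6 v 7 months, background mortality of 3% to 5% a year, and 15% to 30% a year after diagnosis. A true post-diagnosis ratio of 1.25 appears as 1.01 to 1.02. Deaths number 2,058 to 3,459. The design effect is 1 + (32,000/24 − 1) × ICC, which is 14.3 at ICC 0.01 and 2.3 at 0.001. The 95% limits lie a factor exp(1.96 × √(4 × design effect/deaths)) from the estimate: 1.29 to 1.39 at ICC 0.01 and 1.11 to 1.14 at 0.001.

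**The case against.** **The all-nodule sentence may be stray.** Every other statement on survival concerns cancer patients, so one sentence may simply be out of place. This is a fair reading, and deleting the sentence would resolve the mismatch. Against it, H1a also has a claim in cancers and a claim in all nodules, and there the all-nodule claim has a matching sensitivity analysis. Nothing in the documents withdraws the H1c claim.

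**The bias is small.** This stands if times to diagnosis differ only slightly. The shift also roughly halves when deaths are followed to 48 months. The plan promises at least two years of follow-up, so some patients may contribute longer.

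**An all-participant non-inferiority test could reassure falsely.** This stands too. Under the dilution assumptions above, even a doubled hazard after diagnosis appears as only 1.05 to 1.09, below a margin of, say, 1.2 (an example; the plan has none). The plan itself doubts all-nodule denominators because sites may enrol very small nodules differently. That is a reason for an estimate with an interval, without a test.

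**Delayed entry at diagnosis might seem to cure the subset analysis.** It removes the death-free time but not overdiagnosis. In the combined scenarios above it gives 1.04, 1.08 and 1.11, further from 1 than the planned 1.00, 1.03 and 1.07.

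**Censoring of untreated deaths might look like a further error.** A reader might infer that patients who die untreated stay at risk for treatment until the end of follow-up. The documents largely answer this: the Missing Data section says such patients will be censored in time-to-event analyses, and the treatment paragraph allows competing-risk models.

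**Conclusion.** The mismatch is plain on the text: H1c makes a survival claim for all participants with nodules that no objective, endpoint or analysis carries through, and neither survival claim has a margin. H1b is worded as two different tests, and its non-inferiority form also has no margin. The subset analysis conditions on a post-randomisation diagnosis, so a non-inferiority statement from it alone would not rest on randomisation.

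A reader might infer that the planned analysis is tilted materially towards declaring less intensive surveillance non-inferior. The documents do not support that. Death-free time pushes that way and overdiagnosis pushes the other. Without times to diagnosis or mortality, neither the net direction nor the size is known. The figures of 0.96 and 0.98 rest on the assumed 6 v 7 months, exponential times and assumed mortality.

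These are secondary endpoints and the likely bias is small. The priority is low: something the trial could change.

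**What to change.** 1. **Reconcile H1c** across the Hypotheses, Secondary endpoints and H1c analysis sections. Preferably add a Cox analysis of all participants by assigned arm from the index CT, with site clustering as already planned. Report it as an estimate with a 95% confidence interval, alongside completeness of death capture by arm. State that it is heavily diluted and cannot exclude harm in the roughly 3% with cancer. Otherwise delete the all-nodule survival sentence.
2. **Keep the cancer-subset analysis**, label it conditional on a post-randomisation diagnosis, and base no non-inferiority claim on it alone. Because no survival margin was prespecified, present survival as estimation, or label any margin set now as post hoc. Linkage and analysis were scheduled for May 2022 to January 2023, and the current version is dated 7-21-25.
3. **State one test for H1b** in the Hypotheses section, in both timeliness paragraphs and at the end of the time-to-event text, with a margin if it is non-inferiority.

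**Cost.** The text changes are short and add one model, and the survival conclusion becomes less assertive. The main burden is death capture. The Abstract takes survival from membership files and state tumor registries, and tumor registries would not supply deaths of participants without cancer. Sites are to record deaths, but at non-integrated sites those outside the system may be missed. The all-participant comparison is also not perfectly clean, because radiologists enrol patients unblinded after cluster assignment.
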